COVER PAGE

Peri-implant Phenotype, Calprotectin and Mmp-8 Levels in Cases Diagnosed With Periimplant Disease

[name] DDS, PhD¹, [name] DDS, PhD²

¹Bilecik Şeyh Edebali University, Faculty Of Dentistry, Department of Periodontology, Bilecik, Turkey

²Van Yuzuncu Yıl University, Faculty of Dentistry, Department of Periodontology, VAN,

Turkey

Corresponding Author: [name]

Address: Bilecik Şeyh Edebali University, Faculty Of Dentistry, Department of

Periodontology, [name]

E-mail address: [contact] [contact] Office [contact]

[name]

Bilecik Şeyh Edebali University, Faculty Of Dentistry, Department of Periodontology, [name]

E-mail address: [contact] [contact] Office [contact]

[name]

Van Yuzuncu Yıl University, Faculty of Dentistry, Department of Periodontology, VAN,

Turkey

E-mail address: [contact] [contact]

STUDY PROTOCOL AND STATISTICAL ANALYSIS PLAN

Aim of Research: In this study, it was aimed to investigate the effect of peri-implant soft tissue phenotype on the degree of peri-implant disease and its contribution to the results of non-surgical mechanical treatment, accompanied by clinical and biochemical parameters. The research hypothesis is that better clinical outcomes may be achieved in individuals with thicker soft tissue phenotype.

Scientific Basis and Validity of Medical Research:

Over the last two decades, dental implants have been used to replace missing teeth; It has become a widely accepted and applied therapeutic method to support fixed and removable prostheses (1). A dental implant is generally defined as a root form made of titanium that is placed in place of a natural tooth (2).

The soft tissues surrounding dental implants are called peri-implant tissues (peri-implant mucosa). Clinically healthy peri-implant mucosa is pink in color and firm in consistency. However, inflammatory gum diseases can develop around implants, just like natural teeth (3). These diseases are defined as peri-implant diseases. However, a consensus report was published by the European Federation of Periodontology (EFP) and the American Academy of Periodontology (AAP) at the World Workshop on Periodontology (WWP) in November 2017, providing a clear definition with clear clinical distinctions for peri-implant pathologies. It has been determined for both clinical applications and epidemiological studies. According to this consensus report, peri-implant diseases are divided into 4 classes. These conditions are defined as peri-implant health, peri-implant mucositis, peri-implantitis and the presence of peri-implant soft and hard tissue loss (4). Clinically, peri-implant health is characterized by the absence of signs of inflammation and bleeding observed on probing. Peri-implant health can exist around implants with normal or reduced bone support. It is not correct to classify health based on probing depth. Peri-implant mucositis is characterized by bleeding on probing and clinical signs of inflammation. Peri-implantitis is characterized by clinical inflammation occurring in the peri-implant mucosa and subsequent progressive loss of supporting bone. There is radiographic bone loss. Peri-implant soft and hard tissue loss; It is defined as the recession of the mucosa occurring in the implant or peri-implant tissue after the loss of the natural tooth, without evaluating the naturally occurring deficiencies, bone loss in the implant body and the grooves becoming clinically visible (5). Today, the methods used to diagnose peri-implant diseases are plastic probes and dental x-rays, but they may not provide accurate results for a full diagnosis. Bleeding on probing has been a measure of periodontal

inflammation for years, and this is an objective diagnostic finding for the diagnosis of periimplant diseases (6). Despite successful osseointegration and function over the years, dental implants are susceptible to inflammatory peri-implant diseases that affect the supporting tissues and lead to partial or even total loss of osseointegration (7).

Bacterial pathogens (i.e., periodontal pathogens with a similar composition of the oral microbiota that cause chronic periodontitis) represent the primary etiological factor for periimplant diseases. Additionally, an imbalance of individual local inflammatory response and host-parasite interaction is also implicated for the onset of inflammatory peri-implant diseases. Various risk factors (such as poor oral hygiene, smoking, uncontrolled diabetes, genetic characteristics, alcohol consumption and implant surface) play a role in peri-implant tissue destruction. Insufficiency of keratinized mucosa has also been investigated as a possible risk factor for periimplant diseases (8). Phenotype refers to a dimension that may change over time depending on environmental factors and clinical intervention, and may be site-specific. Periodontal phenotype (3-dimensional image of the gingiva) is determined by gingival phenotype (gingival thickness, keratinized tissue width) and bone morphotype (buccal bone thickness) (9). Peri-implant phenotype can be defined as the dimensional, morphological and topographic features that characterize the clinical condition of the tissues surrounding and supporting osseointegrated implants. The peri-implant phenotype encompasses a soft tissue component, including the osseous component characterized by peri-implant keratinized tissue width, mucosal thickness and supracrestal tissue height, and peri-implant bone thickness. This definition applies not only to buccal/facial regions, but also to lingual/palatal peri-implant regions. Like the periodontal phenotype, the peri-implant phenotype is site-specific and may change over time in response to environmental factors (10). Peri-implant mucosa thickness is the horizontal dimension of peri-implant keratinized or non-keratinized soft tissue. Periimplant supracrestal tissue height is the vertical dimension of the soft tissue surrounding a dental implant from the mucosal margin to the crestal bone. Unlike keratinized mucosa width and mucosal thickness, this component of the peri-implant soft tissue phenotype courses circularly around an implant, including proximal regions. Peri-implant bone thickness is the horizontal dimension of the bone tissue supporting the osseotegrated implant. The optimal dimensions of all components of the phenotype to maintain peri-implant tissue health is a controversial issue. However, current studies show that keratinized mucosa, mucosal thickness and periimplant bone thickness are less than 2 mm; confirmed that marginal inflammation is greater in areas where the supracrestal tissue height is less than 3 mm (10). Biomarkers in peri-implant crevice fluid also provide promising results in terms of diagnostic

and prognostic values. A biomarker is a parameter that is objectively measured and evaluated as an indicator of normal biological, pathogenic processes or responses to therapeutic intervention. The imbalance between bacterial load and host response at the soft tissueimplant interface triggers an inflammatory process. Cytokines such as tumor necrosis factor alpha, Interleukin-1-beta, and Interleukin-6 are produced by dendritic cells, connective tissue fibroblasts, macrophages, and neutrophils, as well as a number of enzymes, such as matrix metalloproteinases, by neutrophils, fibroblasts, and osteoclasts, which promote the synthesis of connective tissue collagen, and causes deterioration of alveolar bone. Such cytokines and enzymes can be detected in peri-implant groove fluid by various tests and allow objective evaluation in determining prognosis (11). Nowadays, periodontal and transgingival probing measurement techniques are frequently used to determine gingival thickness. In our study, peri-implant mucosa phenotype will be measured with a newly developed probe (Hu-Friedy Colorvue Biotip Probe®) with a colored tip that will be placed in the gingival sulcus, and the relationship between peri-implant disease and peri-implant phenotype will be investigated. Additionally, since the method to be applied is different, whether it is a reliable method will be compared with the literature and the conventional method (transgingival probing). In our study, connective tissue graft, one of the soft tissue augmentation methods, will be applied to the areas where thin biotypes are detected as a result of our analysis methods. Recent studies (12) have emphasized that soft tissue augmentation procedures applied in areas with periimplant disease can provide significant reductions in bleeding on probing and gingival index values, and in addition, there may be an increase in marginal bone levels. In the light of all this information, the aim of our study is to investigate the effect of peri-implant soft tissue phenotype on the degree of peri-implant disease and its contribution to the results of nonsurgical mechanical treatment, accompanied by clinical and biochemical parameters.

Study Protocol, Methods and Procedures to be Applied: Patient Selection and Study Protocol

The patients to be included in the research will be selected among 50 volunteer individuals aged between 18-65 who applied or were referred to Van Yüzüncü Yıl University Faculty of Dentistry Department of Periodontics with complaints of inflammation in the peri-implant area and were diagnosed with peri-implantitis disease. People who have systemic diseases, smokers, have used antibiotics or received any other medical treatment within 6 months, and are pregnant or breastfeeding will be excluded from the study. Additionally, individuals who

met the definition of peri-implant health and individuals who required surgical treatment of peri-implantitis were excluded from the study.

The peri-implant soft tissue phenotype of all participants who are detected to have periimplant disease and will be included in the study will be measured, necessary clinical and radiological examinations will be performed, necessary samples will be collected and conventional mechanical treatments will be applied. The data of all participants will be collected again in the 6th month following the treatment.

Patient Data Records, Peri-implant Disease Treatment

The details of the application and the research to be conducted will be explained to the patients who will participate in the study, and an informed consent form will be signed. Patients diagnosed with peri-implant disease will be asked for routine examinations before treatment, intraoral photographs will be taken, and clinical and radiological examinations will be performed in detail. Detailed anamnesis of patients who meet the selection criteria will be taken and clinical and radiological examinations will be performed. Patients with caries on their teeth will be directed to Restorative Dentistry Department and restorations of existing caries will be made at the relevant clinic. Before starting their treatment, patients who meet the selection criteria will be given detailed information about periodontal and peri-implant diseases, microbial dental plaque that causes these diseases, and methods of preventing microbial dental plaque. Individuals will be taught how to brush their teeth, how to use an interdental brush.

Peri-implant crevice fluid (PIOS) samples will be collected from all individuals before proceeding with mechanical treatment of diseased implant sites. The areas will be isolated from saliva with cotton pellets, dried with light air, and paper strips (PerioPaper®) will be kept in the trough for 30 seconds (13). Paper strips obtained from each implant will be placed in Eppendorf tubes containing isotonic Ph:7.4 phosphate buffer solution and stored at -40 ° C until analyzed in the laboratory department of our clinic. Routine periodontal parameters such as plaque index (PI) (14), gingival index (GI) (14), bleeding on probing and probing pocket depth scores of the patients whose PIOS samples are collected will be recorded with a Williams-type plastic probe. Following these procedures, the patients' peri-implant phenotype will be evaluated. In the evaluation, the traditional transgingival probing technique and a newly developed technique will be used simultaneously and their correlations with each other

will be examined. A digital caliper with a sensitivity of 0.01 mm will be used to measure transgingival probing values to determine peri-implant mucosa thickness. Measurements will be made from two points: apical of the free gingival sulcus and coronal of the mucogingival junction. After the peri-implant mucosa thickness measurement points are determined with a marker pen, Xylocaine® spray (Vemcaine 10%, lidocaine) or, if necessary, local anesthetic (Maxicaine, lidocaine hydrochloride) will be applied to prevent the patient from feeling pain. Measurements will be made from the marked points in a direction perpendicular to the peri-implant mucosa, using a 10-gauge endodontic spreader (G-Star Medical Co., Ltd., Guangdong, China) with a silicone stopper until its contact with the alveolar bone is felt. Since excessive force will cause the spreader to exceed the soft tissue and advance in the alveolar bone, care should be taken to apply only light forces that can be limited to the soft tissue. After all measurements are repeated twice by the same researcher at 10-minute intervals, the amount of peri-implant mucosa thickness in each region will be determined by taking the average of the two measurements.

If the millimetric values obtained as a result of measurements are less than 1 mm, thin phenotype; If it is more than 1 mm, it will be classified as thick phenotype (15). The second gingival phenotype evaluation in individuals with peri-implant disease will be performed with the Hu-Friedy Colorvue Biotip Probe[®], a newly developed probe with a colored tip that will be placed in the peri-implant pocket. The white probe will first be placed in the peri-implant pocket with a pressure of less than 25 N. If the color of the probe reflects from the gingival tissue, the phenotype will be recorded as thin. If the white color is not visible, the green probe will be placed in the pocket in the same way and if the color is reflected, the phenotype will be classified as medium thickness. If the Green tip is not visible through the gingival tissue, the Blue probe will be used and if the only color seen is Blue, the phenotype will be classified as thick. If blue is not visible, the peri-implant mucosa tissue will be recorded as too thick. Then, traditional mechanical debridement with titanium curettes will be applied to the areas with peri-implant disease without losing the effect of anesthesia. The area will be irrigated with physiological saline from time to time. Following the procedure, patients will be called for control at the 1st, 3rd and 6th months. Oral hygiene instructions will be repeated when necessary. At the 6th month, all clinical parameters examined will be measured again and PIOS samples will be collected again. 6th month following the operation; PIOS samples will be collected again from all operated patients and the clinical parameters examined will be recorded.

Immunohistochemical Analysis

After the target number of patients is reached, the PICF samples collected will be sent to the laboratory for analysis using ELISA (Enzyme-linked immunosorbent assay) kits.

Statistical analysis

Descriptive statistics for the features emphasized will be expressed as Median, Average, Standard Deviation, Minimum and Maximum value. In terms of these characteristics, two-factor and one of the factors repeated-measures analysis of variance will be used to compare group averages and periods (0th month and 6th month). To determine the relationship between variables, Pearson or Spearman correlation coefficients will be calculated separately in the groups. In the calculations, the statistical significance level will be taken as 5% and the SPSS statistical package program will be used for the calculations.

Figure- 1. Clinical Index Form

PLAQUE INDEX

REFERANCES

1 COSGAREA, Raluca; SCULEAN, Anton; SHIBLI, Jamil Avad And SALVI, Giovanni Edoardo. Prevalence Of Peri-İmplant Diseases – A Critical Review On The Current Evidence. Braz. Oral Res. [Online]. 2019, Vol.33, Suppl.1, E063. Epub Sep 30, 2019. ISSN 1807-3107.

5. Caton, J. G., Armitage, G., Berglundh, T., Chapple, I. L. C., Jepsen, S., Kornman, K. S., ... Tonetti, M. S. (2018). A new classification scheme for periodontal and peri-implant diseases and conditions - Introduction and key changes from the 1999 classification. Journal of Clinical Periodontology, 45, S1–S8. doi:10.1111/jcpe.12935

6. NOVAES JUNIOR, Arthur Belém et al. New strategies and developments for periimplant disease. **Braz. oral res.**, São Paulo , v. 33, supl. 1, e071, 2019 . access on 09 June 2020. Epub Sep 30, 2019.

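### The background says thin sites will be grafted, while the aim and procedures describe non-surgical debridement only; the protocol should rule out grafting before month 6 and clear up its undefined operation wording

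*Combined protocol and SAP*

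**What the plan says.** Aim of Research gives the question and the expected direction: "The research hypothesis is that better clinical outcomes may be achieved in individuals with thicker soft tissue phenotype". Scientific Basis and Validity of Medical Research repeats the aim as the effect of phenotype on disease and "its contribution to the results of nonsurgical mechanical treatment". Just before that restatement, the same section says: "In our study, connective tissue graft, one of the soft tissue augmentation methods, will be applied to the areas where thin biotypes are detected". It gives as its reason that augmentation "can provide significant reductions in bleeding on probing and gingival index values".

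Patient Selection and Study Protocol says that, after baseline measurement and sampling, "conventional mechanical treatments will be applied" to all participants. It also says that "individuals who required surgical treatment of peri-implantitis were excluded from the study".

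Patient Data Records, Peri-implant Disease Treatment sets the thickness classes by transgingival probing, thin below 1 mm and otherwise: "If it is more than 1 mm, it will be classified as thick phenotype". It then describes debridement with titanium curettes, control visits at months 1, 3 and 6, and repeat clinical measurement and fluid sampling at month 6. Its last sentence refers to sampling six months after an *operation*, in *operated patients*. No operation is defined.

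Statistical analysis compares group averages at months 0 and 6 by a two-factor analysis of variance with one repeated factor. It names no groups and has no provision for grafted sites.

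**The concern.** The graft sentence is current text, in the future tense and without condition, and it speaks of this study rather than of the literature. Nothing in the procedures carries it out: there is no technique, donor site, date or graft-specific outcome. Nothing withdraws it either.

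The trigger for the graft is thin tissue, which is the exposure whose effect the study wants to estimate. If the sentence were followed before month 6, thin sites would receive debridement plus graft and thick sites debridement alone. The comparison would then not answer the stated question about non-surgical treatment. Two outcomes that the protocol says augmentation may improve, bleeding on probing and gingival index, are recorded at baseline and again at month 6.

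**Working it through.** The plan gives no figure on this point, so there is none to reproduce. The check is a comparison of the texts, followed by the logic of the comparison.

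**1. Is grafting part of the study?**

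| Place | What it supports |
|---|---|
| Aim of Research; restated aim in the background | Non-surgical mechanical treatment only |
| Background, graft sentence | Grafts at thin areas, undated |
| Patient Selection and Study Protocol | Mechanical treatment for all; patients needing surgery for peri-implantitis excluded |
| Patient Data Records, Peri-implant Disease Treatment | Debridement only, then an undefined operation |
| Statistical analysis | Silent |

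The exclusion does not settle the matter. It concerns patients who need surgery for peri-implantitis, and a graft prompted by thin tissue has a different indication. Reference 16, a randomised trial of connective tissue grafting, is listed but not cited in the visible text. That fits a sentence left over from another design, but it is not proof.

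**2. What does the operation wording mean?** Three readings are open: a loose term for debridement, a remnant of a graft plan, or a separate follow-up on its own clock after a later graft. The text does not choose among them, so it cannot be used to show that grafts take place or when.

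**3. What would early grafting do?** Suppose that phenotype is fixed at baseline, thick sites are not grafted and effects add. Let D be the true advantage of thick over thin in the 0-to-6-month change under debridement alone, q the share of thin sites grafted before month 6, and g the mean graft benefit visible at month 6. Then

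observed thick-minus-thin advantage = D − q × g.

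- q = 0 (no grafts, or all after month 6): the observed advantage equals D, so there is no bias from this source.
- q = 1: graft and thin phenotype coincide, and no covariate can separate them.
- q between 0 and 1: graft status varies among thin sites, but the plan does not say that it is recorded, and the ungrafted thin sites may be a selected subset.

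The documents give no value for q, g or the thin/thick split of the 50 patients, so no numerical bias is offered. If g is positive, as the background rationale suggests for bleeding on probing and gingival index, a real advantage of thick tissue would be understated. For plaque index, probing depth and the crevice-fluid markers the protocol states no expected graft effect.

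**4. At what level?** Grafts are announced for areas, and fluid is handled by implant ("Paper strips obtained from each implant will be placed in Eppendorf tubes"), while the hypothesis speaks of individuals. A patient with several implants could therefore have both grafted and ungrafted sites.

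**5. What is untouched?** The baseline association between phenotype and disease, and the comparison of the two thickness methods, use measurements taken before treatment. Neither is affected.

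**The case against.** The strongest reply is that the graft sentence sits in the background, before the heading for study procedures, and that everything under that heading points to debridement alone. On that reading it is one stray sentence and no bias arises. This may well be right, and it is why the point is framed as an inconsistency rather than a design flaw. But the document states no rule that the procedures override the background, and a site team could follow the sentence as written.

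It can also be said that the harm needs several unshown conditions: grafts are done, they precede month 6, and the unnamed groups in Statistical analysis are thin and thick. This stands. The phenotype grouping is inferred from the hypothesis and the 1 mm classification; the aim also covers degree of disease, so other groupings are possible.

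A reader might go further and infer that the thin-versus-thick comparison will be biased against the hypothesis, or that the mention of operated patients shows grafting within the follow-up. The documents support neither. The rationale says only that augmentation can reduce bleeding and gingival index, with no time frame. A graft shortly before month 6 might show no benefit yet, or a healing effect. The operation wording may simply mean debridement.

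**Conclusion.** The inconsistency is certain: the protocol announces grafts at thin sites that its aim and procedures do not contain, and it refers to an operation that it never defines. The consequence is conditional. If thin sites are grafted before the month-6 measurement, any thin-versus-thick comparison of 0-to-6-month change mixes phenotype with graft, and it does so completely if every thin site is grafted. For bleeding on probing and gingival index this could mask an advantage of thick tissue. Size and direction cannot be established from the documents, and the bias is absent if no grafts are done or if they follow month 6. The point should be fixed because the correction is cheap and an early graft could not be undone in the analysis.

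**What to change.** If grafting is not part of the study, delete the graft sentence from the background and add a positive statement to the procedures, for example: *No soft-tissue grafting is performed at study sites before the month-6 assessment.* Deletion alone would not say this.

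If grafting is intended, schedule it after the month-6 assessment, say so in the procedures, and keep post-graft data out of the phenotype comparison.

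In the same edit, replace *operation* and *operated patients* in Patient Data Records, Peri-implant Disease Treatment with *debridement* and *treated patients*, or define them as a separate post-graft follow-up with its own timing.

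The first route costs only wording and loses no data. The second makes thin sites wait six months for a graft, and graft outcomes then need the separate follow-up just mentioned if they are to be reported.

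### Does selecting only peri-implantitis cases conflict with an aim about the degree of peri-implant disease?

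*Combined protocol and SAP*

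**What the plan says.** The title describes biomarker "Levels in Cases Diagnosed With Periimplant Disease". Aim of Research, repeated at the end of the scientific background, is to study the "effect of peri-implant soft tissue phenotype on the degree of peri-implant disease" and how phenotype contributes to the results of non-surgical mechanical treatment, using clinical and biochemical parameters. The background also says that "the relationship between peri-implant disease and peri-implant phenotype will be investigated".

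Scientific Basis and Validity of Medical Research gives the classification: "According to this consensus report, peri-implant diseases are divided into 4 classes". These are health, mucositis, peri-implantitis, and soft and hard tissue loss. It describes the two inflammatory conditions separately. "Peri-implant mucositis is characterized by bleeding on probing and clinical signs of inflammation"; peri-implantitis adds "subsequent progressive loss of supporting bone. There is radiographic bone loss".

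Patient Selection and Study Protocol contains the only sentence that sets a diagnosis for inclusion: 50 volunteers aged 18 to 65 "with complaints of inflammation in the peri-implant area and were diagnosed with peri-implantitis disease". It then says that individuals who "met the definition of peri-implant health and individuals who required surgical treatment of peri-implantitis were excluded from the study". The following paragraphs, and the phenotype and treatment text under Patient Data Records, Peri-implant Disease Treatment, use the general term peri-implant disease. Clinical and radiological examinations are planned for all participants. Statistical analysis compares unspecified groups at month 0 and month 6 and names no diagnosis term.

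**The concern.** Of the four classes in the background, one is included by name (peri-implantitis), one is excluded by name (health), and two (mucositis, and soft and hard tissue loss) have no stated eligibility. If peri-implantitis is already required, excluding health removes nobody, which could hint that a wider population was meant. Bone loss separates mucositis from peri-implantitis, yet no threshold or reading method is given.

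Each reading would carry a cost. If only peri-implantitis is enrolled, mucositis is missing at the mild end and surgical cases at the severe end, so a statement about the degree of peri-implant disease in general would go beyond the sample. If mucositis is enrolled as well, the sample mixes two diagnoses. Phenotype is measured, not randomised. If one phenotype had more mucositis, and mucositis responded differently to debridement, an unadjusted phenotype comparison would carry that difference, and a larger sample would not remove it.

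**Working it through.** The plan gives no figure to reproduce: the 50 participants come without a power calculation, effect size or SD. The check is first one of text, then of size under assumptions.

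**Text**

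1. *Inclusion sentence against title and aim.* Peri-implantitis is one of the peri-implant diseases in the plan's own classification. The general term used elsewhere is therefore true of everyone the inclusion sentence admits. The wording differs in breadth, not in truth.
2. *Exclusion of health.* It is redundant if peri-implantitis is required. It is also nearly redundant on the wider reading, because participants must present with complaints of inflammation and the background characterises health by the absence of inflammatory signs. A complaint is not a clinical sign, so the redundancy there is not complete, but the exclusion does little to tell the readings apart. The companion exclusion, of peri-implantitis needing surgery, fits the narrow reading equally well.
3. *Degree.* The aim says it is assessed with clinical and biochemical parameters. Plaque index, gingival index, bleeding and probing depth are recorded, and the title names calprotectin and MMP-8. These can grade severity within peri-implantitis.
4. *Bone level.* The recorded parameters are introduced as examples and are taken with a probe, so the absence of bone level from that list does not show that it goes unrecorded. Detailed radiological examination is planned separately. What is truly unstated is the criterion.
5. *Groups.* Statistical analysis does not define them. The hypothesis about thicker tissue suggests phenotype groups, but the text does not fix this.

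**Size, on the wider reading only**

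None of these inputs is in the documents. Assumed: two phenotype groups of 25; mean mucositis share 0.5; share differing between groups by d = 0.10, 0.20 or 0.40; diagnoses differing in 6-month change by g = 0.3, 0.5 or 1.0 within-diagnosis SD; no phenotype effect given diagnosis; two-sided 5% test.

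- Shift in the group difference = d × g.
- SE = √((v₁ + v₂)/25), with v = 1 + g² × p(1 − p) and p the group's mucositis share.
- Chance of p < 0.05 from the noncentral t distribution with 48 df and noncentrality shift/SE.

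Middle case, d = 0.20 and g = 0.5: shares 0.6 and 0.4, v = 1 + 0.25 × 0.24 = 1.06, SE = √(2.12/25) = 0.291, shift 0.10, ratio 0.34, chance 6.3%.

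Extreme case, d = 0.40 and g = 1.0: shares 0.7 and 0.3, v = 1 + 0.21 = 1.21, SE = √(2.42/25) = 0.311, shift 0.40, ratio 1.29, chance 24.3%.

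| d | g = 0.3 | g = 0.5 | g = 1.0 |
|---|---|---|---|
| 0.10 | 5.1% | 5.3% | 6.1% |
| 0.20 | 5.5% | 6.3% | 9.5% |
| 0.40 | 7.0% | 10.4% | 24.3% |

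The shift exceeds one standard error only in the bottom right cell. With groups of 35 and 15 the range is 5.1% to 21.1%.

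**The case for a change.** The strongest contrary case is that a reader cannot be certain which population the results will describe. The eligibility paragraph is loosely written, mucositis is never mentioned after the background, and without a written bone-loss criterion the diagnosis may be hard to reconstruct afterwards. Clarifying all this would be cheap: an eligibility statement, a case definition drawn from examinations already planned, and perhaps one extra model.

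The textual part stands: eligibility of mucositis and of soft and hard tissue loss is unstated, and no bone-loss criterion is given. But the sentence that governs enrolment is explicit, and the remaining requests either write down detail or change the design. Admitting mucositis would make the sample more heterogeneous, which is a trade-off and not a correction. A model with and without diagnosis has a purpose only if two diagnoses are enrolled, which the documents do not establish. Even then, the shift computed above is bias only if diagnosis confounds the comparison. If diagnosis expresses the degree of disease, part of that shift belongs to the effect the aim sets out to study.

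**Conclusion.** The wording is looser than it should be, but the plan needs no change on this point. Taken as written, it studies peri-implantitis not requiring surgery, and its results are interpretable for that population. The cost is scope: conclusions about degree of disease extend to severity within that class and not to a contrast with mucositis. The documents give no severity distribution, so the loss of range cannot be quantified. The case definition, and whether any mucositis cases were in fact enrolled, are details that investigators would ordinarily state when describing the sample.

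The numerical risk rests on a reading that departs from the inclusion sentence, on phenotype groups that the analysis section does not define, and on assumed shares and response gaps. It stays near 10% or below in eight of nine scenarios. If both diagnoses turned out to have been enrolled, the matter would have to be looked at again, with diagnosis considered as either confounder or mediator; nothing in the documents shows that this will happen.
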